2.1. Study Design

This study is a 12 month open label extension study of PF-02545920 20 mg dosed BID following study A8241021.

The study includes a Screening visit (V1) to assess eligibility followed by a Baseline visit (V2) and visits after 2 weeks, 4 weeks, 3 months, 6 months, 9 months, and 12 months of treatment. The final scheduled visit is a Follow-up visit 7-14 days after the last dose. Screening visit (V1) and Baseline visit (V2) will coincide with Week 19 and Week 26 Visits from study A8241021, respectively. For the Screening visit (V1) and Baseline visit (V2) procedures and assessments, the investigator will use data collected during Week 19 and Week 26 visits for study A8241021, respectively. Subjects, who meet study entry criteria, will be assigned to the 20 mg BID dose. During the 12-month treatment phase, subjects will return for study assessments at Week 2 (V3), Week 4 (V4), Month 3 (V5), Month 6 (V6), Month 9 (V7), Month 12 (V8), and for a Follow-up visit (V9).

Subjects, who were assigned to the 20 mg PF-02545920 dose group in the preceding A8241021 study, will continue to receive 20 mg PF-02545920 in this study without any titration. All other subjects will be titrated to the 20 mg BID dose as follows: 5 mg BID for 7 days, 10 mg BID for 7 days, 15 mg BID for 7 days, then 20 mg BID for the remainder of the treatment phase. Titration is in place to reduce incidence of AEs, frequent monitoring is in place for neutropenia, and an option for de-escalation by 5 mg decrements (temporary or permanent) will be available should the investigator consider the AE intolerable.

Subjects who are discontinued (Early Termination) at or after Day 14 should complete as many of the Month 12 (V8) assessments as possible. Subjects should return to complete the Follow-up visit whenever possible.

Based on the total number of 260 subjects expected to be randomized in study A8241021, up to 260 subjects may take part in this open label extension. CCI

CC1
CC1 (CC1) CCI CCI.

2.2. Study Objectives

Primary Objective:

- To assess long-term safety and tolerability of 20 mg BID of PF-02545920 in subjects with HD.*

Secondary Objectives:

- To assess motor function after 6 and 12 month oral dosing with 20 mg BID of PF-02545920 in subjects with HD.*
- To assess the efficacy of 6 and 12 month oral dosing with 20 mg BID of PF-02545920 on chorea severity in subjects with HD.*

- *To assess whether 6 and 12 month oral dosing with 20 mg BID of PF-02545920 can improve overall clinical impression in subjects with HD.*

CCI [REDACTED] :

- CCI [REDACTED]
- [REDACTED]
- [REDACTED]
- [REDACTED]
- [REDACTED]
- [REDACTED]
- [REDACTED]

3. INTERIM ANALYSES, FINAL ANALYSES AND UNBLINDING

No interim analysis will be performed in the study.

3.1. CCI [REDACTED]

CCI [REDACTED]

4. HYPOTHESES AND DECISION RULES

4.1. Statistical Hypotheses

The primary trial variables examine long-term safety and tolerability of therapy with 20 mg BID of PF-02545920. The primary analysis of long-term safety will be focused on Adverse events, weight, vital signs (pulse, blood pressure and body temperature), electrocardiogram (ECG), clinical laboratory findings (hematology, biochemistry and urinalysis), suicidal ideation and behavior (SIB) assessments and white blood count (WBC) and absolute neutrophil count (ANC). No formal statistical hypothesis will be conducted for the primary trial variables.

The secondary efficacy variables are:

- *Change from baseline in the Total Motor Score (TMS) assessment of the Unified Huntington Disease Rating Scale (UHDRS) after 6 and 12 months of treatment.*
- *Change from baseline in the Total Maximum Chorea (TMC) score of the UHDRS after 6 and 12 months of treatment.*
- *Clinical Global Impression-Improvement score after 6 and 12 months of treatment.*

Change from baseline in change in TMS and TMC will be calculated, decreases indicate improvement. The null hypothesis is that the change from baseline to a certain time-point is greater or equal to 0. The corresponding alternative hypothesis is that change from baseline to a certain time-point is less than 0. If the true mean change from baseline is denoted by μ then the hypothesis tested will be:

$$\begin{aligned} H_0: \mu &\geq 0 \\ H_a: \mu &< 0 \end{aligned}$$

For *Clinical Global Impression-Improvement* (CGI-I) score a lower score indicates improvement. The null hypothesis is that the CGI-I value at a certain time-point is greater or equal to 4 (no change to very much worse). The corresponding alternative hypothesis is that the CGI-I value to a certain time-point is less than 4 (very much improved to minimally improved). If the true mean change from baseline is denoted by μ then the hypothesis tested will be:

$$\begin{aligned} H_0: \mu &\geq 4 \\ H_a: \mu_{PF} &< 4 \end{aligned}$$

Both the change from baseline for all subjects (pooled) and by three cohorts (defined by dose level in A8241021 study: PF-20mg, PF-5mg, or Placebo) will be analyzed.

Statistical hypotheses for exploratory endpoints will be specified in a similar fashion as above.

4.2. Statistical Decision Rules

All one-sided tests for secondary and exploratory endpoints are described as to be performed using the nominal alpha-level of 0.025, this corresponds to a two-sided test with alpha-level of 0.05. In addition to the p-values, two-sided 95% confidence intervals will be provided.

5. ANALYSIS SETS

5.1. Full Analysis Set

All efficacy endpoints will be evaluated over the Full Analysis Set (FAS), which is the set of subjects who have an open label extension study baseline efficacy evaluation and have completed at least the Week 2 visit with a valid UHDRS TMS score, and took ≥ 1 dose of open-label study medication. Subjects without post-dose measurements will not contribute to the analysis, except in the description of the baseline values.

5.2. 'Per Protocol' Analysis Set

No Per Protocol analysis will be conducted.

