5.1. Allocation to Treatment

The investigator's knowledge of the treatment should not influence the decision to enroll a particular subject or affect the order in which subjects are enrolled.

Investigators will use an Interactive Response Technology (IRT) to assign a unique subject identification number to each subject who has signed the informed consent document (ICD). This identifying number will be retained throughout the duration of the study participation. Subject eligibility for participation in the study will be determined following the Screening assessments (V1). Once the subject is determined to be eligible for treatment, the investigator will obtain a randomization number and study medication assignment utilizing the IRT.

Subjects, who received PF-02545920 20 mg BID in the preceding A8241021 study, will continue to receive PF-02545920 20 mg BID in this study. Subjects, who previously received either PF-02545920 5 mg BID or placebo in the A8241021 study, will be titrated to PF-02545920 20 mg. The titration will start at 5 mg BID and the dose will be increased by 5 mg BID every 7 days, up to a 20 mg BID to be reached at Day 22, and maintained until Month 12 (V8). Subjects will take 4 tablets twice a day provided in blister packs from Baseline Day 1 (V2) to Week 4 (V4) and in bottles from Week 4 (V4) to Month 12 (V8). For subjects, who have been de-escalated from 20 mg BID to lower dose in the preceding study A8241021, the investigator should contact the sponsor study clinician and medical monitor to discuss titration scheme.

Table 3. Allocation to Study Treatments

Treatment Group	Study Treatment	Drug Administration	Duration
20 mg PF-02545920, Subjects receiving 20 mg PF-02545920 in the preceding A8241021 study	Days 1-365 Four 5 mg tablets of PF-02545920	Orally, BID	12 months (Days 1-365)
20 mg PF-02545920, All other subjects	Days 1-7 One 5 mg tablet of PF-02545920 Three placebo tablets for PF-02545920 Days 8-14 Two 5 mg tablets of PF-02545920 Two placebo tablets for PF-02545920 Days 15-21 Three 5 mg tablets of PF-02545920 One placebo tablet for PF-02545920	Orally, BID	12 months (Days 1-365)
	Days 22-365 Four 5 mg tablets of PF-02545920		

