6.2.8. Early Termination Visit

Subjects who withdraw or are withdrawn from the study should undergo an early termination visit whenever possible, unless consent for participation is also withdrawn, in which case no further study related procedures should be performed (see Subject Withdrawal).

In case of Early Termination between Baseline Day 1 and Day 14 (exclusive), only safety assessments will be performed (no efficacy assessments). If Early Termination occurs after Day 14 (inclusive), as many Month 12 (V8) assessments as possible should be completed.

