9. DATA ANALYSIS/STATISTICAL METHODS

Detailed methodology for summary and statistical analyses of the data collected in this study will be documented in a statistical analysis plan (SAP), which will be maintained by the sponsor. This document may modify the plans outlined in the protocol; however, any major modifications of the primary endpoint definition and/or its analysis will also be reflected in a protocol amendment.

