9.2. Efficacy Analysis

All endpoints will be evaluated over the Full Analysis Set (FAS), which is the set of subjects who have an extension study baseline efficacy evaluation, took ≥1 dose of open-label study medication. Subjects without post-dose measurements will not contribute to the analysis, except in the description of the baseline values.

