6.8.5. Clinical Global Impression of Severity/Improvement (CGI-S/CGI-I)

The CGI-S/CGI-I is a global measure of severity of illness (CGI-S) and improvement or change (CGI-I) based on the clinician's assessment of all available clinical data obtained from interviewing the subject.

The CGI-S consists of a single 7-point rating score of illness severity that is based on how ill the subject is relative to other subjects he/she has had experience with. Raters select one response based on the following question, "Considering your total clinical experience with this particular population, how ill is your subject at this time?" Scores are: 1, Normal, not ill at all; 2, Borderline ill; 3, Mildly ill; 4, Moderately ill; 5, Markedly ill; 6, Severely ill; or 7, Among the most severely ill subjects.

The CGI-I consists of a single 7-point rating of total improvement or change from baseline CGI-S, regardless of whether or not the change is due entirely to drug treatment. Raters select one response based on the following question, "Compared to your subject's condition at the beginning of treatment, how much has your subject changed?" Scores are: 1, Very much improved; 2, Much improved; 3, Minimally improved; 4, No change; 5, Minimally worse; 6, Much worse; or 7, Very much worse.

The CGI-S/CGI-I rater can have access to all clinical information related to subject severity and change, and does not need to be independent of other assessments. However, the rater who assesses the initial CGI-S should be the clinician who rates overall change via the CGI-I during the study.

The CGI-S will be performed at Baseline Day 1 (V2). The CGI-I will be administered at Month 6 (V6), Month 12 (V8), and in case of early termination. This assessment will be administered by a trained rater from the site investigational team (eg, clinician).

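### SAP 5.1 makes a valid Week 2 TMS a condition of the FAS, so as written it can drop subjects who have Month 6 or Month 12 ratings (minor)

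*SAP*

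**What the plan says.** SAP 5.1 sets one population for all efficacy analyses: "All efficacy endpoints will be evaluated over the Full Analysis Set (FAS"). Three conditions are joined by a plain conjunction: an extension baseline efficacy evaluation, at least one open-label dose, and that subjects "have completed at least the Week 2 visit with a valid UHDRS TMS score". The section then adds: "Subjects without post-dose measurements will not contribute to the analysis, except in the description of the baseline values". SAP 8.1 and the summary table in SAP 8.5 apply this set to TMS, TMC and CGI-I.

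Protocol 9.2 defines the FAS as "the set of subjects who have an extension study baseline efficacy evaluation" and who took at least one dose. It has the same closing sentence about subjects without post-dose data, but no Week 2 or TMS condition. On the status of the SAP, protocol section 9 says: "This document may modify the plans outlined in the protocol". A protocol amendment is needed only for major changes to the primary endpoint or its analysis.

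The secondary endpoints are at Months 6 and 12 (SAP 4.1 and 6.8). TMS is rated at each visit from Week 2 to Month 12 and at early termination, and TMC is taken from its items (SAP 6.8.1). For CGI-I, SAP 6.8.5 says: "The CGI-I will be administered at Month 6 (V6), Month 12 (V8), and in case of early termination". The SAP 8.5 table lists missing data as excluded for all three endpoints.

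**The concern.** A full analysis set should not depend on a post-randomisation or post-enrolment measurement unless the analysis needs that measurement. Here it does not. A change from baseline at Month 6 or 12 uses the baseline value and the value at that visit, and CGI-I uses only the rating at that visit. A subject who missed the Week 2 visit, or attended without a valid TMS, but was rated at Month 6 or 12 has everything these tests require. Read as written, SAP 5.1 still removes that subject from all of them.

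What is at stake is avoidable loss of observed data, selection on an early visit that is not an endpoint, and a definition that two programmers could implement differently. The FAS decides who enters every TMS, TMC and CGI-I summary and test. It has no role in the safety set, which SAP 5.3 defines by one dose alone.

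**Working it through.** The plan gives no figure that depends on the FAS condition. The total of up to 260 is the expected enrolment of the preceding study (protocol sections 3 and 9.1), not a power calculation. The main check is therefore logical, followed by an illustration of size.

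**Step 1. Who is treated differently?** Take subjects with a baseline efficacy evaluation and at least one dose, and exclude missing data as in SAP 8.5.

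| Subject | SAP 5.1 FAS | Protocol 9.2 FAS | In a Month 6 or 12 test under SAP / protocol FAS |
|---|---|---|---|
| Leaves before Day 14 | out | in | no / no |
| No valid Week 2 TMS, leaves before Month 6 | out | in | no / no |
| Valid Week 2 TMS, leaves before Month 6 | in | in | no / no |
| Valid Week 2 TMS, rated at Month 6 or 12 | in | in | yes / yes |
| No valid Week 2 TMS, rated at Month 6 or 12 | out | in | **no / yes** |

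Only the last row differs in the tests. The clause is not needed to keep out very early leavers. For termination before Day 14, protocol 6.2.8 says "only safety assessments will be performed (no efficacy assessments"), so these subjects have no post-baseline efficacy value to analyse.

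**Step 2. Which analyses?** SAP 8.2.1 runs paired t-tests on all subjects and on three groups: 2 scales × 2 time points × (1 pooled + 3 groups) = 16 tests. The CGI-I one-sample tests at 2 time points use the same set.

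**Step 3. How large?** The documents give no rate of missing Week 2 TMS among subjects rated later. Let p be that share (assumption) and N = 260 (the maximum). Subjects lost = N × p. Ratio of confidence interval widths = 1/√(1 − p).

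| p (assumed) | N × p | Lost | Kept | Width ratio |
|---|---|---|---|---|
| 1% | 2.6 | 3 | 257 | 1.005 |
| 2% | 5.2 | 5 | 255 | 1.010 |
| 5% | 13.0 | 13 | 247 | 1.026 |
| 10% | 26.0 | 26 | 234 | 1.054 |

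If the removed subjects' mean change differs from that of the rest by δ SD (also an assumption), the pooled mean moves by p × δ:

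- low: 0.01 × 0.25 = 0.0025 SD
- high: 0.05 × 1.0 = 0.05 SD

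For comparison, the half-width of the 90% interval named in SAP 8.1 and 8.2.1 is t(0.95, 259)/√260 = 0.102 SD. The extreme corner, p = 10% with δ = 1.0, gives 0.10 SD. It would need 26 subjects who lacked the Week 2 rating and still reached Month 6 or 12. With fewer than 260 subjects at those visits, the interval is wider and the same shift matters less.

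**The case against.** The strongest defence has three parts.

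1. The phrase may have meant that a subject stayed long enough to have a first post-baseline rating. That would be an ordinary rule and would exclude nobody with a later rating. This is plausible, but the text names the Week 2 visit and no other SAP section readmits a subject who missed it.
2. The affected group is likely to be very small. Study drug is dispensed and ANC/WBC are checked at Week 2 (protocol 6.2.2), so a subject who skipped the visit and still reached Month 6 would be unusual. SAP 7 queries missing scale responses. This stands as an argument about size. It does not remove the problem: a query cannot create a rating for a missed visit, and protocol section 7 accepts that some required tests will not be feasible.
3. These are secondary endpoints in an uncontrolled open-label study. This also stands, and it limits the severity.

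A reader might infer four stronger points, which the documents do not support.

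- *The SAP breaches the protocol.* Protocol section 9 allows the SAP to modify the plan, and the FAS is not part of the primary safety analysis.
- *SAP 5.1 contradicts itself*, because its next sentence provides for subjects without post-dose data. That sentence can be applied endpoint by endpoint. A subject with a Week 2 TMS who leaves before Month 6 may have no post-dose value on a scale rated only at Baseline, Month 6 and Month 12. The sentence also stands in protocol 9.2.
- *The clause is a failed attempt to select for exposure to the target dose*, since for titrated subjects protocol 5.1 has the dose rising "up to a 20 mg BID to be reached at Day 22", after the Week 2 visit. No passage offers exposure as the reason, so there is nothing to rebut.
- *The condition was added after termination.* The amendment log dates an FAS update to 15 Feb 2017, which is 61 days after the 16 Dec 2016 cut-off in SAP 8.1. It does not say which words changed, so the date does not show that the Week 2 condition was new.

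**Conclusion.** The point holds as a minor one. As written, SAP 5.1 selects on a post-baseline rating that none of the Month 6 or Month 12 tests needs. Given the missing-data rule in SAP 8.5, its only possible effect on those tests is to remove subjects who have the rating. This rests on reading the clause literally; if a first post-baseline rating at any visit was meant, the fault is in the wording alone.

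The number affected and the direction of any bias cannot be derived from the documents. Under the assumed 1% to 5%, about 3 to 13 of 260 subjects would be lost and the pooled mean would move by at most 0.05 SD, about half the 90% half-width of 0.102 SD. A reader might infer that the efficacy results are materially biased; nothing in the documents shows that. The primary safety variables are unaffected.

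**What to change.** In SAP 5.1, delete the Week 2 TMS condition and use the protocol FAS: an extension baseline efficacy evaluation and at least one open-label dose. State that each visit's analysis uses the subjects who have a rating at that visit. If the sponsor prefers a post-baseline condition, requiring at least one valid post-baseline efficacy rating at any visit gives the same Month 6 and Month 12 tests, because anyone rated at those visits meets it.

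Report, pooled and for each of the three groups, how many subjects the deleted condition would have removed.

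The cost is one sentence of SAP text and a small change to the population flag, with no new data. The downside is that n will differ slightly by visit and some FAS members will contribute only to the description of baseline.

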5.3. Safety Analysis Set

All subjects who entered the extension study with at least one dose of study medication will be included in the safety analyses.

5.4. CCI

CCI

5.5. Treatment Misallocations

Subjects who are undergoing the titration phase and do not titrate in the intended order will be reported under the dose level they actually received.

5.6. Protocol Deviations

The criteria and determination of protocol violation/deviations will be determined by Pfizer prior to database release.

6. ENDPOINTS AND COVARIATES

6.1. Safety Endpoint(s)

Primary Endpoints: In this section, the safety endpoints that will be measured during the study are detailed. Where applicable, details of the endpoints to be derived and definition of baseline are also provided.

The following data are considered in standard safety summaries (see protocol for collection days and list of parameters):

- The number and proportion of subjects with adverse events.
- Assessment of clinical laboratory parameters.

- Assessment of vital signs.
- Assessment of ECG parameters.
- White blood count (WBC) and absolute neutrophil count (ANC) at each visit.
- Abnormal laboratory findings from baseline.
- Frequency and severity of adverse events related to extrapyramidal symptoms (EPS) including dystonia and akathisia, as assessed by the investigator.
- C-SSRS (suicide severity assessment).
- Adverse events, weight, vital signs (pulse, blood pressure and body temperature), physical examination, neurological examination, electrocardiogram (ECG) and clinical laboratory findings (hematology, biochemistry and urinalysis). The endpoints are:
 - The number and proportion of subjects with adverse events.
 - Assessment of clinical laboratory parameters.
 - Assessment of vital signs.
 - Assessment of ECG parameters.
 - White blood count (WBC) and absolute neutrophil count (ANC) at each visit.
 - Abnormal laboratory findings from baseline.
 - Frequency and severity of adverse events related to extrapyramidal symptoms (EPS) including dystonia and akathisia, as assessed by the investigator.
 - C-SSRS (suicide severity assessment).

6.2. Adverse Events

All AEs occurring during the course of the study will be coded using the most current MedDRA coding dictionary.

All AEs (serious and non-serious) reported from the first day of study treatment through and including 28 calendar days after the last administration of the study drug will be considered treatment emergent AEs (TEAEs).

6.3. Laboratory Safety Tests

Safety laboratory tests will be performed as described in the protocol.

To determine if there are any clinically significant laboratory abnormalities, the haematological, clinical chemistry (serum) and urinalysis safety tests will be assessed against the criteria specified in the sponsor reporting standards. The assessment will take into account whether each subject's test result is within or outside the laboratory reference range for the particular laboratory parameter.

Assessment results collected at Week 26 for Study A8241021 will be used for Baseline Day 1.

6.3.1. WBC and Neutrophil Monitoring

WBC counts with differential will be recorded or performed at each study visit starting with Baseline Day 1 (V2). The results of these assessments will be reviewed by the investigator as soon as possible once they are available, but no later than 2 business days after receipt of the lab results. After reviewing the results, the investigator must confirm and document that the WBC and/or ANC do not meet stopping criteria (See Protocol Section 3.1) for the subject to continue in the study.

6.3.2. Neutropenia Assessment

Subjects who meet any of the “subject stopping criteria” or the study stopping criteria for WBC or ANC should receive a hematology consultation and assessment for all potential etiologies of the WBC and ANC findings. This assessment should adhere to clinical standard of care for evaluation of neutropenia, but at a minimum include the following assessments: clinical assessment for infections and physical examination; review of relevant past medical history, prior concomitant medications, and prior WBC and ANC counts when available; repeated complete blood count with WBC, ANC, and a peripheral blood smear; bone marrow sampling for subjects who have an ANC <500 unless medically contraindicated or otherwise unobtainable. Additional assessments indicated by the standard of care for evaluation of neutropenia should be pursued in accordance with the investigator's and consultant's judgment.

